13.6 Reporting and Exclusions

To be evaluable for the primary endpoint, a patient needs to (1) meet the eligibility criteria, (2) receive erlotinib for 7 days (range 5-14 Days), (3) have EGFR staining at baseline in the surgical cohort (such that they could have a reduction in EGFR over the 7 day intervention period), (4) need their EGFR assessed post-baseline, and (5) taken 85% of the scheduled doses (6 of 7 days) and must have taken the dose on the day of liver resection (prior to liver resection surgery). Participants with erlotinib administration outside of the target duration will not be considered evaluable for the primary endpoint.

Sub-analyses for the different endpoints may be performed on the subsets of participants, excluding those for whom major protocol deviations have been identified (e.g., early death due to other reasons, early discontinuation of intervention, major protocol violations, etc.). However, sub-analyses will not serve as the basis for drawing conclusions concerning efficacy, and the reasons for excluding participants from the analysis will be clearly reported. There will be no imputation for missing data. A summary and listing of all major protocol violations will be provided. All details will be given in the final study report and/or manuscript. Participants lost to follow-up will be censored on the last date of assessment (or contact) and as appropriate for analyses that are dependent upon length of study participation.

13.7 Evaluation of Toxicity (Secondary endpoint)

All participants will be evaluable for adverse events (AEs) from the time of their first dose of erlotinib through completion of their post-intervention evaluation.

All AE analyses will be carried out at each dose level. The maximum grade for each type of adverse event will be recorded for each participant and frequency tables will be reviewed to determine the overall patterns. The number and severity of adverse events will be tabulated and summarized across all grades. Grade 3+ adverse events will be similarly described and summarized separately. As per NCI CTC Version 4.0, toxicities are defined as adverse events that are classified as either possibly, probably, or definitely related to the interventional agent. Overall toxicity incidence, as well as toxicity profiles will be explored and summarized. Frequency distributions, graphical techniques and other descriptive measures will form the basis of these analyses. In addition, we will review all adverse event data that are graded as 3, 4, or 5 and classified as either “unrelated or unlikely to be related to the study intervention in the event of an actual relationship developing.

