4. Day 1 only: For women of childbearing potential only, a negative pregnancy test must be documented prior to initiation of study agent. This test does not have to be repeated on Day 1 if the first study agent dose is within 7 days of baseline test.
5. Liver biopsy must take place after pre-registration and after all other screening procedure, but before Registration.
6. For the Surgical cohort A only, submission of biopsy specimens is not required prior to registration/randomization. However, the CPN Pathology Coordinator, [name], must be notified that the pre-intervention biopsy did occur so that she can confirm readiness for registration.
7. First dose of erlotinib must take place ≤ 14 days after registration.
8. Final dose of erlotinib will be taken on the day of surgery/biopsy but before laboratory tests and before administration of anesthesia for surgery/biopsy.

9. Post-intervention evaluation may begin on the day prior to surgery/biopsy, if more convenient. If a clinical pre-surgery/pre-anesthesia evaluation takes place and the data are available, then it may replace the scheduled physical exam and vital sign assessment. Collection of study agent, medication diary, final AE assessment, and WIWI questionnaire may occur on the day prior to surgery/biopsy, the day of surgery/biopsy, or at the time of early termination as long as they are complete before administration of anesthesia for surgery/biopsy. Final dose of erlotinib must be taken with a sip of water before blood is drawn for labs and research and before administration of anesthesia for surgery/biopsy.
10. Study team will attempt to contact the participant by phone, text message, or email (per participant's preference) to remind them to take their study medication.
11. For non-surgical cohort, if phospho-EGFR assessment is negative, participant will not proceed to Screen 2B.
12. After informed consent and pre-registration, specimen from previous clinical biopsy will be obtained and submitted to Mayo Clinic for phospho-EGFR assessment (see Section 10.2.2.2).
13. To be eligible for the primary endpoint, study agent must be taken for 5-14 days (ideally 7 days), with final dose of study agent and post-intervention specimen collection taking place on the day of surgery/biopsy prior to blood tests and surgery/biopsy (ideally Day 7).
14. Reminder: The Quantitative RNA test for this study should be performed only if the HCV antigen test is positive.

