7.5 Evaluation at Completion of Study Intervention

The participant will undergo a brief physical exam with vital signs. If institutional standards of care include a physical exam and this information is available to the study team, then the clinical physical exam will suffice. This evaluation may occur on the day prior to surgery/biopsy or prior to administration of anesthesia on the day of surgery/biopsy. Any remaining study agent supply and completed medication diary will be collected. The final assessment of adverse events and recording of concomitant medications will occur during this evaluation. Participants will be asked to complete the Was It Worth It (WIWI) questionnaire.

The final dose of erlotinib will be taken on the day of surgery/biopsy (prior to the procedure) with a sip of water. After the final erlotinib dose and prior to surgery/biopsy, repeat research blood draw and laboratory evaluations including blood chemistry (HBV, HCV, INR, Total bilirubin, ALT, AST, BUN, Creatinine, Alkaline phosphatase, Creatine phosphokinase, Calcium, Total protein, Albumin, quantitative HCV RNA [only if HCV+], and hematology (CBC with 5-part differential, platelets). Note that HBV and HCV do not have to be repeated at the post-intervention evaluation if the screening test results were negative/undetectable.

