7.6 Post-intervention Follow-up Period

Immediately following the liver resection operation or liver biopsy, portions of liver from the resected specimen will be collected and processed for study (See Section 10 for details).

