7.7.2 Post-Intervention

For surgical cohort participants, liver resection surgery and post-surgical observation should follow institutional standards of care and good clinical practice. After liver resection, a portion of the liver specimen that does not contain tumor and consists of at least 1 gram of liver tissue will be placed in RNAlater (Qiagen). One other section of non-tumor bearing liver tissue measuring at least 1 cm x 1 cm x 0.5 cm will be placed in formalin and stored in the refrigerator.

Non-surgical cohort participants will undergo a post-intervention percutaneous or transjugular biopsy of their cirrhotic/fibrotic liver in a non-tumor bearing area. Participants should remain NPO after midnight before the scheduled biopsy to allow for use of conscious sedation if indicated. Whether to perform the biopsy under local anesthesia or under conscious sedation will be at the discretion of the clinician performing the biopsy. For percutaneous biopsies, a 16-gauge core is preferable; an 18-gauge core is acceptable. All participants will be monitored post-procedure according to institutional standards of good clinical practice, after which time they may be discharged to home. Percutaneous biopsy may be conducted under ultrasound guidance. Whether by percutaneous or transjugular approach, biopsies will consist of a minimum of 2 samples. Four (4) samples is preferable. The first two samples will be placed in formalin. The second two will be placed in RNAlater (Qiagen). The four samples will be stored in a refrigerator. If the clinician performing a percutaneous biopsy is unable to obtain the first two core biopsies safely (e.g. participant starts bleeding), the clinician should abort the attempt. The participant will be considered not evaluable.

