11.2.3 Follow-up of SAE

Site staff should send follow-up reports as requested when additional information is available. Additional information should be entered on the DCP SAE form in the appropriate format. Follow-up information should be sent to DCP as soon as available.

AEs and SAEs that are on-going at the time of the final AE assessment (post-intervention evaluation) will be treated according to institutional standards of good clinical practice.

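### Section 13.7 closes the adverse-event window before the biopsy or resection, so the planned tables omit later events and no scheduled contact looks for them

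*Combined protocol and SAP*

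**What the plan says.** Section 13.7 sets the analysis window: "All participants will be evaluable for adverse events (AEs) from the time of their first dose of erlotinib through completion of their post-intervention evaluation".

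Section 7.5 says of that evaluation: "This evaluation may occur on the day prior to surgery/biopsy or prior to administration of anesthesia on the day of surgery/biopsy". It adds: "The final assessment of adverse events and recording of concomitant medications will occur during this evaluation". Footnote 9 to the schedules of events allows some flexibility in when the final AE assessment is done, but only "as long as they are complete before administration of anesthesia for surgery/biopsy".

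Dosing runs later than that. Section 7.5: "The final dose of erlotinib will be taken on the day of surgery/biopsy (prior to the procedure) with a sip of water". The procedure follows. Under 7.7.2, "Non-surgical cohort participants will undergo a post-intervention percutaneous or transjugular biopsy of their cirrhotic/fibrotic liver in a non-tumor bearing area"; section 3 describes this as a research biopsy. Cohort A has its resection.

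In both schedules (7.1 and 7.2) the adverse-event row has its last entry under the post-intervention evaluation and none in the final column. Section 7.6, although headed as a follow-up period, provides only that "portions of liver from the resected specimen will be collected and processed for study". Section 11.2.3 treats the same visit as the end of AE assessment: "AEs and SAEs that are on-going at the time of the final AE assessment (post-intervention evaluation) will be treated according to institutional standards".

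**The concern.** Participants are on erlotinib when the liver is biopsied or resected, and the AE window has already closed. Section 6.2 reports altered coagulation and bleeding with erlotinib. Section 4.3.2 admits participants with platelets down to 50 x 10^9/L and INR up to 1.5. A bleed after an on-drug liver biopsy is therefore a plausible AE to which the drug may have contributed. Section 11 counts untoward events as AEs whether or not the drug caused them, so a procedural origin is no reason to leave such an event out.

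Section 13.5 promises a complete AE profile, and the primary objective asks for a dose that is safe as well as effective. Following 13.7 as written, the tables would show no post-procedure events whatever their true frequency. Section 2.3 expects the results to define the dose schedule for later randomized prevention studies, so readers of those tables need to know where observation stopped.

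**Working it through.** The plan gives no figure on this point, so there is none to reproduce. The first two steps compare timings; the third is an illustration under assumed rates.

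**1. Order of events on the procedure day**
- Final AE assessment: the day before, or the same day before anesthesia (7.5, footnote 9).
- Last erlotinib dose: the same day, before the blood draw and before anesthesia (7.5, footnotes 8 and 9).
- Biopsy or resection (7.7.2).
- After the procedure: care and monitoring by institutional standards (7.7.2) and tissue collection (7.6). No AE contact is scheduled.

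Scheduled AE follow-up after the procedure is therefore zero days for every participant; the target accrual is 31 (13.3, Amendment 9).

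**2. Day-before option**

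If the final assessment is on Day 6 of a 7-day course, one dosing day has no symptom check: 1/7 = 14%. Over the permitted 5 to 14 days this is 1/5 = 20% to 1/14 = 7%. Laboratory values are not lost, because blood is drawn after the last dose (7.5).

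**3. Effect on the safe-dose decision**

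Rule in 7.4.2: 0 or 1 DLT in 5 is safe. With 2 or 3 in 5, another 5 are entered and the dose is safe if the total is below 33%, that is, at most 3 of 10. With 4 or 5 in 5 the dose is above the maximum tolerated dose.

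Assumptions (the documents give neither rate): d = 10% have a DLT during dosing; q = 0, 5% or 10% have a DLT-level event after the procedure, independently. If all are counted, p = 1 - (1 - d)(1 - q).

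With X and Y independent Bin(5, p) for the first and second five:

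P(safe) = P(X ≤ 1) + P(X = 2) P(Y ≤ 1) + P(X = 3) P(Y = 0)

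| q | p | P(X ≤ 1) | P(X = 2) P(Y ≤ 1) | P(X = 3) P(Y = 0) | P(safe) |
|---|---|---|---|---|---|
| 0 | 0.100 | 0.9185 | 0.0729 x 0.9185 = 0.0670 | 0.0081 x 0.5905 = 0.0048 | 0.990 |
| 5% | 0.145 | 0.8443 | 0.1314 x 0.8443 = 0.1110 | 0.0223 x 0.4569 = 0.0102 | 0.965 |
| 10% | 0.190 | 0.7576 | 0.1918 x 0.7576 = 0.1453 | 0.0450 x 0.3487 = 0.0157 | 0.919 |

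The q = 0 row is also the result when post-procedure events occur but none reaches the count. The largest shift is thus from 99.0% to 96.5% (about 2.5 points) or to 91.9% (about 7 points). It is an upper limit for two reasons: it supposes that no post-procedure DLT is ever reported, and it applies q to every participant in a cohort of five, as if all had the research biopsy.

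**The case against.** The strongest reply is that serious events are already caught elsewhere. Section 11.1.1 requires AEs to be recorded after consent and baseline and sets no stop date. SAE reporting (11.2) has none either. Section 7.4.2 sets no DLT time window and makes every DLT an SAE, reportable within 24 hours. Section 13.7.1 has all grade 4 and 5 events reviewed. Biopsy participants are monitored before discharge, so an acute serious bleed would probably be known to the site. This stands. A reader might infer that on-drug biopsy complications never reach the trial's safety data; the documents do not support that.

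A second reply is that the window is defensible. Section 13.1 ties the AE endpoint to the 7-day intervention period, 8.2 speaks of an overall rather than a complete profile, and stopping before resection keeps surgical events from swamping drug effects. This stands in part. It supports tabulating post-procedure events separately, but not leaving them out, and it does not cover Day 7 symptoms missed under the day-before option.

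Third, the Master DSMP cited in 12.4 is not among the documents and may add follow-up. That cannot be excluded.

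Two other inferences are tempting. One is to use only the first look at five participants, where the safe call drops from 92% to 84% or 76%; that ignores the second five in 7.4.2 and overstates the effect two- to threefold. The other is to read the median onsets in 6.2 (8 days for rash, 12 for diarrhea) as events lost to the window. Those come from continued 150 mg dosing in lung cancer and do not show how many events begin after a 7-day course ends.

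**Conclusion.** The gap is real but modest. As written, 13.7 excludes from the secondary-endpoint tables all events after the biopsy or resection and, with the day-before option, Day 7 symptoms. No scheduled contact looks for them. The likely loss is mainly mild, moderate or late events and their tabulation, because serious and DLT-level events have open-ended reporting routes. The open-ended recording in 11.1.1 and the closed window in 13.7 also need to be reconciled.

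The effect on the safe-dose call is at most 99.0% against 96.5% or 91.9%. That rests on an assumed 10% DLT rate during dosing, an assumed 5% or 10% afterwards, independence, and none of the later events being counted.

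A reader might infer that the Amendment 9 statement of no DLTs is unreliable. The documents do not show that: they show only that the scheduled checks behind it end before the procedure. All of this holds subject to what the Master DSMP says.

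**What to change.** - **13.7:** end AE evaluability a fixed short time after the last dose, for example 14 days. That length is a choice; it matches the post-drug contraception period in 4.1.5. Keep the present tables and add a separate table of post-procedure events by cohort and dose level.
- **7.1 and 7.2:** add one AE phone contact at that time.
- **7.4.2:** state that drug-related post-biopsy events meeting the DLT grades count in Cohort B within the window. Send Cohort A post-resection events of grade 3 or higher to the medical monitor for review rather than counting them automatically. With no DLTs and no cohort repeated under Amendment 9, this part has little practical force now.
- **Participants already treated:** abstract post-procedure events from the source documents listed in 12.3.
- **If none of this can be done:** replace the word *complete* in 13.5 and report that the AE profile and the safe-dose call stop before the procedure.

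Cost: one call per participant, an amendment approved by DCP and the IRBs (14.3), possibly a case report form change (12.2), and one extra table. No drug or further procedure is needed. A dose decision could wait up to 14 days, but enrollment already pauses after every five participants (7.4.3). The downsides are noisy attribution after resection and, for past participants, dependence on what the charts recorded.

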8.4 Off-Agent Criteria

Participants may stop taking the study agent due to: completion of the planned intervention period, development of an adverse event or serious adverse event, inadequate agent supply, noncompliance, use of concomitant medications, medical contraindication, refusal, ineligibility (see Section 8.5), major treatment violation (see Section 8.5) or alternative treatment. Participants will continue to be followed, if possible, for safety according to the intended schedule of events (see Section 7).

Participants discontinuing the planned intervention prematurely will be encouraged to complete the Post-Intervention Evaluation tests and procedures as appropriate (if participant does not refuse, is not lost to follow-up, or unless it is clinically contraindicated). See Section 8.5 for further details as to data submission for participants deemed Ineligible after starting treatment or classified as a Major Treatment Violation (i.e., protocol requirements regarding intervention during the first week post-randomization were severely violated).

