11. REPORTING ADVERSE EVENTS

DEFINITION: AE means any untoward medical occurrence associated with the use of a drug in humans, whether or not considered drug related. An AE can therefore be any unfavorable and unintended sign, symptom, or disease temporally associated with participation in a study, whether or not related to that participation. This includes all deaths that occur while a participant is on a study.

Please note that all abnormal clinical laboratory values that are determined to be of clinical significance based on a physician's assessment are to be reported as AEs. Those labs determined to be of no clinical

significance or of unknown clinical significance (per the physician's assessment) should not be reported as AEs. Any lab value of unknown clinical significance should continue to be investigated/followed-up further for a final determination, if possible.

A list of AEs that have occurred or might occur (Reported Adverse Events and Potential Risks) can be found in §6.2, Pharmaceutical Information, as well as the Investigator Brochure or package insert.

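### In the supplied documents, liver-test worsening that is not judged clinically significant reaches no planned safety summary, although the panel is scheduled before and after treatment

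*Combined protocol and SAP*

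**What the plan says.** **What is analysed.** Section 13.7 counts all participants as evaluable for adverse events "from the time of their first dose of erlotinib through completion of their post-intervention evaluation". Its outputs, by dose level, start from this rule: "The maximum grade for each type of adverse event will be recorded for each participant". Number and severity, Grade 3 and above, and treatment-related events are then tabulated. The reviews in 13.7.1 (dose-limiting toxicities, Grade 4 and Grade 5 events) are also of adverse events.

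**Which labs become adverse events.** Section 11 states that "all abnormal clinical laboratory values that are determined to be of clinical significance based on a physician's assessment are to be reported as AEs". Labs judged to be of no clinical "significance or of unknown clinical significance (per the physician's assessment) should not be reported as AEs". For the unknown group it adds: "Any lab value of unknown clinical significance should continue to be investigated/followed-up further for a final determination, if possible".

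**What is measured.** Sections 7.1 to 7.3 schedule INR, total bilirubin, ALT, AST, alkaline phosphatase, albumin and creatinine at screening. Section 7.5 repeats them: "After the final erlotinib dose and prior to surgery/biopsy, repeat research blood draw and laboratory evaluations including blood chemistry". Note 9 to the schedules allows the "final AE assessment, and WIWI questionnaire may occur on the day prior to surgery/biopsy". For participants who stop the drug early, 8.4 says: "Participants will continue to be followed, if possible, for safety according to the intended schedule of events".

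**Where paired change is planned.** Section 13.5 plans change from baseline for the translational markers, including viral load. It names no liver test.

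**The concern.** The secondary objective in Section 1 is the relation between erlotinib dose-schedule and side effects in people with cirrhosis. Section 6.2 says that transaminase rises without symptoms occur on erlotinib, and it names cirrhosis and viral hepatitis among the factors complicating severe hepatic dysfunction. A symptom-free rise in someone whose liver tests are already abnormal could plausibly be judged not clinically significant. Such a rise would be measured by schedule and then appear in none of the outputs planned in these documents.

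Section 13.4 says the primary and secondary results will be used to plan a larger study. Below the clinical-significance filter, the hepatic part of what is handed on would rest on individual physicians' judgement in an open-label trial, not on the measured change.

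**Working it through.** The plan gives no figure on this point, so there is none to reproduce. The check sets the sections side by side, followed by short arithmetic.

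**1. Following a lab value through the plan**
- Judged clinically significant: reported as an adverse event (Section 11), so it enters the 13.7 tables.
- Judged of no significance: not reported, so it enters no output in 13.7 or 13.7.1.
- Judged of unknown significance: not reported unless follow-up, where possible, settles it.
- Section 13.5 does not pick up the last two groups, and no other section summarises the pairs.

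**2. Does the timing of the final assessment widen the gap?** Only slightly. The schedules place the post-treatment labs within the post-intervention evaluation, so the draw falls inside the 13.7 window. The day-before option in note 9 adds a minor risk that a result arrives after the adverse event review.

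**3. Why the baseline value is needed.** Section 4.3.2 admits ALT up to 5 x ULN. Section 6.2 gives ALT Grade 2 as >2.5 to 5.0 x ULN and Grade 3 as >5.0 to 20.0 x ULN. The values below are invented examples inside the entry limit:

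| ALT before (x ULN) | ALT after (x ULN) | Ratio | Grade after |
|---|---|---|---|
| 1.0 | 4.9 | 4.9/1.0 = 4.90 | 2 |
| 2.6 | 4.9 | 4.9/2.6 = 1.88 | 2 (also 2 before) |
| 4.9 | 5.1 | 5.1/4.9 = 1.04 | 3 |

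The post-treatment grade does not rank these by size of change. A listing based on grade shift alone would flag the third row (4% rise) and miss the second (88% rise). A fold criterion of 1.5 would catch the second.

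**4. Age of the baseline.** Screening labs may precede registration by 14 days (note 1), and the first dose may follow registration by 14 days (note 7). The last dose of a 14-day course falls 13 days after the first. The maximum is 14 + 14 + 13 = 41 days before the post-treatment draw. For a 7-day course it is 14 + 14 + 6 = 34 days.

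**5. How much a listing can say.** If none of n participants worsens, the one-sided 95% upper bound on the true proportion is 1 - 0.05^(1/n):
- n = 5 (evaluable goal per dose level, 13.3): 0.451, or 45%
- n = 10 (planned enrolment per dose level, 13.3): 0.259, or 26%
- n = 31 (target accrual under Amendment 9, a best case): 0.092, or 9%

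**The case against.** The strongest reply is that the plan analyses the endpoint it defines. The secondary endpoint is the adverse event profile; laboratory change is not an endpoint, and viral load gets a paired analysis because it is a listed translational endpoint. That stands: this is an omission, not an inconsistency between 13.5 and 13.7.

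Second, the serious harm is already covered. Significant lab changes must be reported and followed whether or not related, and related Grade 3 or higher events other than rash are dose-limiting (7.4.2). That also stands, and it confines the point to what lies below the filter. A reader might infer that significant liver injury goes unrecorded; Section 11 says the reverse. The ALT examples show why a grade needs its baseline. They do not show that a physician would dismiss a 4.9-fold rise.

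Third, the values are scheduled anyway and could be summarised at reporting. True, but nothing in these documents commits anyone to do so, and note 3 requires upload only of registration documents for some tests.

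Fourth, Section 12.4 defers detail to a master safety monitoring plan, and 12.1 cites a master data management plan. Neither was available. A reader might infer that no laboratory summary is planned anywhere; the documents do not support that.

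Finally, a reader might infer that unreported labs could have let an unsafe dose pass. The documents give no rate of unreported abnormal labs, so any such calculation would rest on invented rates. Section 13.3 reports no dose-limiting toxicities under Amendment 9.

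**Conclusion.** The point holds in a limited form. In the supplied documents, measured liver-test worsening that a physician does not judge clinically significant reaches no planned summary, although the tests are scheduled before and after treatment. The number of participants affected is unknown.

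This is a worthwhile, inexpensive improvement to the safety reporting of a trial in cirrhosis. It does not undermine the primary analysis, the toxicity rule or any dose decision. Confidence is moderate, because the conclusion assumes that neither master plan already provides the summary. If one does, 13.7 need only refer to it.

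The added output would be modest in strength. Even with all 31 participants measured and none worsening, a true proportion of up to 9% would remain compatible with the data, and up to 45% at a dose with five.

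**What to change.** Add to 13.7, for everyone who took at least one dose, by dose level and overall, regardless of adverse event reporting:

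1. As the core, median and range of paired change for bilirubin, ALT, AST, INR, albumin and creatinine, expressed as a ratio to baseline for ALT, AST and bilirubin.
2. A descriptive shift table of CTCAE v4 grade from baseline to post-treatment.
3. A listing of each participant who worsens by one grade or more, or whose ALT, AST or bilirubin rises by a prespecified fold (for example, to 1.5 times baseline or more), with whether it was reported as an adverse event and its attribution.
4. The number with no post-treatment value, and why.

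State the limits with the table. It is descriptive and uncontrolled. It cannot show a dose relation: per-dose numbers are too small and the pooled row mixes doses. The baseline may be up to 41 days old, and in Cohort A the research biopsy falls between the two draws. Flag anticoagulant users in the INR rows, because 4.2.8 and 5.5 provide for holding or bridging these drugs.

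The cost is one more table and one listing, plus abstraction of existing lab reports if the values are not in the database; note 3 does not name albumin or the post-treatment panel. Entry limits, the toxicity rule, visits and blood draws stay as they are.
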